2.5.3 Handling of missing values/censoring/discontinuations

Subjects with missing monthly migraine day data at week 52 of treatment, and subjects that discontinue initially assigned treatment prior to the week 52 visit will be imputed as non-responders (not achieving a net benefit).

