- a) The summary of discontinuations for initially assigned treatment and last available switched treatment will be provided by due to COVID-19 and non-COVID-19 reasons.
- b) In light of COVID-19 pandemic and its potential impact on treatment effect, an important scientific question of interest to address is to estimate the treatment effect had COVID-19 pandemic not occurred.
 - The target population is defined by all subjects in the study who received at least one dose of study treatment.
 - The variable of interest is reduction in MMD from baseline to week 52 on initially assigned treatment.
 - The intercurrent event describes how events that may occur after randomization are considered when assessing the treatment effect

- Discontinuation of initially assigned treatment due to non COVID-19 related reason: Subjects who discontinue due to non COVID-19 related reasons prior to week 52 will be considered as non-responders.
- Discontinuation of initially assigned treatment due to COVID-19 related reason (hypothetical strategy): All MMD data up to discontinuation of initially assigned treatment will be used. Ignore all the MMD data after treatment discontinuation and impute MMD data till week 52 using missing at random approach (MAR). The discontinuation reason due to COVID-19 pandemic will be identified from the defined COVID-19 protocol deviations.
- The summary measure is the odds ratio between two treatment arms. It will be obtained by CMH test similar to primary endpoint analysis. A subject will be responder if subject has at least 50% reduction in MMD from baseline at week 52 and completed initially assigned treatment for one year; otherwise subject will be a non-responder.

c) Summary statistics will be provided for change from baseline in MMD for subjects with COVID-19 infection separate for before and after COVID-19 infection period. The information about whether subject has COVID-19 infection is collected on AE CRF.

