2.7.4 Sensitivity / Supplementary analyses

Sensitivity analysis for secondary endpoint:

To assess impact of missing values on interpretation of results sensitivity analyses will be performed for secondary endpoint "Cumulative average change from baseline on the monthly migraine days during the treatment period week 4 to week 52 (Months 1-12)". Missing MMD data will be imputed using multiple imputation under MAR assumption. The multiple imputation model will be build based on similar subjects in the same treatment arm.

Supplementary analysis for secondary endpoint:

The supplementary analysis for secondary endpoint "Cumulative average change from baseline on the monthly migraine days during the treatment period week 4 to week 52

(Months 1-12)" is defined considering hypothetical strategy for subjects who are discontinuing early or switching initially assigned treatment.

This analysis will evaluate what if subject would have continued initially assigned treatment for 52 weeks

- if subject discontinues initially assigned treatment and does not switch to other SoC then missing data after discontinuation will be imputed using MAR. This is because we are considering what if subject would have continued initially assigned treatment.

- if subject switched to other SoC drug then for switched period until week 52 data will be considered as missing and such missing data will be imputed using MAR.

Points to note:

- The off-treatment MMD data and MMD data from switched drug cannot be used for analysis since it will not represent MMD values under initially assigned treatment.
- If MMD data is available say up to week 36 then data will be imputed from week 40 till week 52.

Table 2-5 Summary of secondary efficacy endpoints and analysis methods

Endpoint	Analysis	Imputation
Proportion of subjects completing the study at Month 12 on the initially assigned treatment	A Cochran-Mantel-Haenszel (CMH) test stratified by number of prior prophylactic migraine medication failures (1 vs. 2) will be used under a 2-sided significance level of 0.05.	No imputation.
Cumulative average change from baseline on the monthly migraine days during the treatment period week 4 to week 52 (Months 1-12)	The change from baseline will be analyzed using a linear mixed effects repeated measures model including treatment group, baseline value, stratification factor(s), scheduled visit, and the interaction of treatment group with scheduled visit.	No imputation.

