5.1.4.3.2 Multiple imputation sensitivity analyses steps

The following steps are followed in order to create the structure of the analysis dataset where missing values and appropriate variables could be imputed.

- Obtain subject id, treatment group, stratification factor, sex, race group, age group, BMI group (subjid trt01pn mmstratn sexn race agemedn bmimedn) from ADBS, ADSL.
- Obtain number of prior migraine prophylactic treatment failed, baseline disease duration group (prophfln durmedn) from ADBS.
- Obtain avisitn paramcd param aval avalc base chg dtype from ADATTACK
- Perform minor data manipulation, as required, to reinstate the missing data, eg if dtype="LOCF" then aval=,, avalc="" " and chg=.

- Ensure the baseline values are included in the chg variables before data transformation, eg if avisitn=2000 is baseline then chg=base;
- Transpose all the data so you have one observation per subject and each visit becomes a variable within its own right, eg rows where avisitn=2004, 2008, 2012 etc become the column week4, week8, week 12 etc.
- Impute the missing data for MAR according to the methods in next steps

MAR multiple imputations steps:

Note that the some variable has missing values and there is a mix of categorical and continuous variables in the modelling of the missing data. Therefore, fully conditional specification (FCS) methods are employed within proc mi to impute the missing data.

- FCS logistic is used for dichotomous variables (mmstratn sexn agemedn bmimedn prophgrp durmedn); discrim is used for categorical variables with more than 2 categories (race); regpmm is used for continuous variables (wk0, wk4, wk8,... wk52).
- wk4, wk8 , ... and wk52 represent the chg variable for each of the visits respectively, and wk0 is baseline.

MAR modeling step:

- For the primary endpoint, first, define 50% Responders based on imputed MMD data under the assumption of MAR. Then, use the same method as for primary variable - the stratified CMH test to get estimates for numbers of responders in each treatment group and odds ratio at week 52 for each dataset.
- For change from baseline in MMD it is used a linear mixed effects model on imputing data under the assumption of MAR. There is no gaps in imputed data, therefore, all the data is available to analyze and can use a fixed effects model looking only at the avisitn=2052/week52 data.

MAR combining step:

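### COVID-19 supplementary analysis of net benefit (SAP 2.5.4, item b): the responder rule still requires one-year completion, so imputing migraine days for COVID-related discontinuers cannot change their response status

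*SAP*

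**What the plan says.** SAP 2.5.4, COVID-19 item b, states its aim as to "estimate the treatment effect had COVID-19 pandemic not occurred". It treats two intercurrent events differently:

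- Discontinuation for other reasons: "Subjects who discontinue due to non COVID-19 related reasons prior to week 52 will be considered as non-responders".
- COVID-related discontinuation of initially assigned treatment is given a hypothetical strategy. MMD up to discontinuation is kept, and then: "Ignore all the MMD data after treatment discontinuation and impute MMD data till week 52 using missing at random approach (MAR".

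The summary measure is an odds ratio from the CMH test. A responder needs at least a 50% MMD reduction "from baseline at week 52 and completed initially assigned treatment for one year; otherwise subject will be a non-responder". No exception follows.

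The population also differs from that of the primary analysis, which uses the full analysis set (FAS). For item b: "The target population is defined by all subjects in the study who received at least one dose of study treatment".

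The primary rule in SAP 2.5.3 is that "subjects that discontinue initially assigned treatment prior to the week 52 visit will be imputed as non-responders".

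**The concern.** Two parts of the same analysis conflict. The strategy for COVID-related discontinuers matters only if their imputed Week 52 MMD can make some of them responders. The responder sentence rules that out, because completion is a separate condition that these subjects fail by definition. Both strategies then end in the same classification.

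Item b is the only planned analysis that yields a COVID-adjusted odds ratio for net benefit. Item a tabulates discontinuations by reason, and item c summarises MMD before and after infection. If item b comes out close to the primary result, a reader could take that as evidence that pandemic-related stopping did not matter, although the rule prevents such stopping from having any influence.

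**Working it through.** **1. The plan's own figure, used as the base for the illustration.** Inputs from SAP section 3: control rate 0.18, odds ratio 2, 394 and 197 subjects, two-sided 0.05, 90% power.

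- Erenumab odds = 2 × 0.18/0.82 = 0.4390, so the rate is 0.4390/1.4390 = 0.305. The difference is 0.125 (the SAP says 12%).
- Continuity-corrected CMH power, assuming the same rates in both strata: h = 394 × 197/591 = 131.33; mean difference term h × 0.1251 = 16.43; null SD = √(131.33 × 0.2634 × 0.7366) = 5.048; alternative SD = 131.33 × √(0.305 × 0.695/394 + 0.18 × 0.82/197) = 4.712.
- Power = Φ[(16.43 − 0.5 − 1.96 × 5.048)/4.712] = Φ(1.28) = 0.90. The stated 591 reproduces.

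**2. The responder rule applied by type of subject.** Responder = (MMD change ≤ −50%) AND (completed one year on initially assigned treatment).

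| Subject | Primary analysis | Item b as written |
|---|---|---|
| Stops, not COVID-related | non-responder | non-responder |
| Stops, COVID-related | non-responder | non-responder for any imputed MMD |
| Completes, Week 52 MMD observed | decided by MMD | decided by MMD |
| Completes, Week 52 MMD missing | non-responder | not stated; could be imputed |
| Never dosed | non-responder in the FAS | outside the population |

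For a COVID-related discontinuer, imputed changes of −100%, −75%, −50%, −25% and 0% all return non-responder, because the completion condition is false each time.

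**3. Does another section supply the missing rule?**

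- SAP 5.1.4.3.2 says to "define 50% Responders based on imputed MMD data under the assumption of MAR". It imputes MMD and is silent on completion, so it does not override item b's own sentence.
- SAP 2.5.4, in the text introducing the MAR sensitivity analysis, points the other way. Because the endpoint is composite, it confines imputation to subjects who complete 52 weeks and lack a Week 52 MMD value.
- SAP 2.7.4 has a hypothetical analysis: "This analysis will evaluate what if subject would have continued initially assigned treatment for 52 weeks". It concerns the secondary MMD change, which has no completion condition, and covers discontinuers whatever their reason.

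None of these sets or imputes completion for COVID-related discontinuers.

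**4. Illustrative size.** The documents give no COVID discontinuation counts, so the shares are assumed. Suppose shares cE (erenumab) and cC (control) stop for COVID and would otherwise have had the design rates. Under the rule as written the rates become (1 − cE) × 0.3051 and (1 − cC) × 0.18. The target stays at 0.305 vs 0.18, odds ratio 2.00.

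| cE / cC | Rates as written | Odds ratio |
|---|---|---|
| 2% / 2% | 0.299 vs 0.176 | 1.99 |
| 5% / 5% | 0.290 vs 0.171 | 1.98 |
| 10% / 10% | 0.275 vs 0.162 | 1.96 |
| 5% / 0% | 0.290 vs 0.180 | 1.86 |
| 0% / 5% | 0.305 vs 0.171 | 2.13 |
| 10% / 5% | 0.275 vs 0.171 | 1.83 |
| 5% / 10% | 0.290 vs 0.162 | 2.11 |

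Example, first row: (0.2990/0.7010)/(0.1764/0.8236) = 1.99. With equal shares the distortion is small. With imbalance it can go either way.

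**The case against.** The best defence is that this is a wording gap. Labelling the strategy hypothetical, and giving the other discontinuers a separate rule, implies that completion is removed as an obstacle for COVID-related discontinuers; the last sentence merely restates the general definition, and a programmer would probably query it. That is very likely the intent. It is not what is written, though, and the closing clause that makes everyone else a non-responder excludes it. The implied reading is also incomplete, since it does not say whether these subjects are taken to have completed or might later have stopped for another reason. Protocol 1.1 cites one-year retention of 75–80% on erenumab and persistence of 13–16% on oral prophylactics (the latter from chronic-migraine claims data, so only indicative). The choice is therefore not obviously neutral between arms.

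Two stronger inferences are tempting and are not supported:

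- *That item b must reproduce the primary responder counts or odds ratio.* It excludes never-dosed subjects and may impute completers with missing Week 52 MMD. Assumed example near the design rates: 120/394 vs 35/197 gives (120/274)/(35/162) = 2.03. If 8 and 4 such completers exist and half are imputed as responders, 124/394 vs 37/197 gives (124/270)/(37/160) = 1.99.
- *That treating completion as met bounds the odds ratio.* For given imputed MMD it is an upper limit on each arm's rate only. Assumed example from the same base: 10 and 3 COVID-related discontinuers are imputed to a 50% reduction, giving 130/394 vs 38/197 and (130/264)/(38/159) = 2.06. If 90% and 50% of them would have completed, 129/394 vs 36.5/197 gives (129/265)/(36.5/160.5) = 2.14. That lies outside the interval from 2.03 to 2.06.

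It is also fair that item a and the pandemic summaries in SAP 2.3.1 will show how many subjects are involved. That limits the risk of misreading but does not make item b estimate its stated target.

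**Conclusion.** The contradiction is real and follows from the text of item b alone. As written, imputing MMD for COVID-related discontinuers changes no response status, so item b cannot estimate the no-pandemic effect as far as that effect acts through COVID-related discontinuation. This holds on the literal rule, without any assumption about rates.

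The numerical consequence is unknown. The illustrative range (about 1.96 to 1.99 with equal shares of 2–10%, about 1.83 to 2.13 with imbalance, against 2.00) rests on assumed shares and on COVID-related discontinuers having the design rates had they stayed.

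The defect is confined to one supplementary analysis. It should not be read as a criticism of the primary result: the primary test, its alpha and the sample size of 591 are untouched. The point is worth correcting but not critical.

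**What to change.** 1. Amend the responder sentence of item b so that the completion condition does not apply as observed to subjects whose discontinuation of initially assigned treatment was COVID-related.
2. Pre-specify how completion is set for them. Either treat it as met, so that response follows imputed Week 52 MMD, or impute it together with MMD by arm, so that later stopping for other reasons remains possible. The first is simpler and sufficient to remove the contradiction; the second is optional.
3. If completion is treated as met, state that this gives an upper limit for each arm's responder rate and is not a bound on the odds ratio.
4. Reconcile the earlier sentence in SAP 2.5.4 that limits imputation to subjects completing 52 weeks, for instance by confining it to Sensitivity analysis I.
5. In the same edit, say whether item b imputes completers with missing Week 52 MMD, and note that its population is dosed subjects rather than the FAS, so that differences from the primary result can be interpreted.

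The cost is a few lines of SAP text and, for the second option, an additional imputation model. The downside is one added assumption about completion, in a supplementary analysis only.

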2.5.5 Sensitivity analyses with corrected stratification factor

The sensitivity analyses will be performed by deriving the correct stratification factor for subjects who have been mis-stratified. Such subjects can be identified by PD criteria as specified below:

- For subjects with a INCL06 PD = 0 treatment failure (TF) (These subjects should be excluded from analysis as not in strata 1 or 2)
- For Subjects with a EXCL04 PD = 3 (or greater) TF (These subjects should be excluded from analysis as not in strata 1 or 2)
- For subjects with assigned (IRT) strata of TF1 (but have a TRT07 PD present), correct strata = TF2
- For subjects with assigned (IRT) strata of TF2 (but have a TRT07 PD present), correct strata = TF1

Analysis for primary endpoint will be repeated using corrected strata.

2.5.6 Sensitivity analyses excluding subjects taking non-approved medications or prohibited medications or polytherapy

Subjects who have taken non-approved medications or prohibited medications or polytherapy (data is identified using protocol deviations) during initially assigned treatment are excluded from sensitivity analysis for primary endpoint. The analysis for primary endpoint will be repeated after excluding these subjects.

2.6 Analysis of the key secondary objective

There is no key secondary objective.

2.7 Analysis of secondary efficacy objective(s)

2.7.1 Secondary endpoints

The secondary efficacy variables are as listed below and respective definitions of responders / non-responders are added in subsequent sections:

- Proportion of subjects completing the study at Month 12 on the initially assigned treatment
- Cumulative average change from baseline in monthly migraine days during the treatment period week 4 to week 52 (Months 1-12)
- Proportion of responders as measured by PGIC at month 12 on the initially assigned treatment

2.7.2 Statistical hypothesis, model, and method of analysis

Analysis of above mentioned secondary endpoint will utilize the FAS.

- Proportion of subjects completing the study at Month 12 on the initially assigned treatment

The responders and non-responders for this endpoint are defined as given below:

Subjects who complete one year on the initially assigned treatment are considered as responders.

A subject will be considered as a non-responder if a subject do not complete one year on the initially assigned treatment. This includes (a) subjects who discontinue initially assigned treatment permanently (b) subjects who switched to oral prophylactics other than initially assigned treatment.

In subjects with episodic migraine, the proportion of subjects completing 12 months on initially assigned treatment will be compared between the AMG334 treatment group and oral prophylactics group, in terms of odds ratio. Thus, below hypothesis will be tested between initially assigned treatment groups:

Null hypothesis: Odds ratio =1 vs Alternative hypothesis: Odds ratio \neq 1.

A Cochran-Mantel-Haenszel (CMH) test stratified by number of prior prophylactic migraine medication failures (1 vs. 2) will be used under a 2-sided significance level of 0.05. The p-value of the test, and the estimated odds ratio between AMG334 and active comparator, as well as its 95% confidence interval, will also be reported.

- Cumulative average change from baseline on the monthly migraine days during the treatment period week 4 to week 52 (Months 1-12)

The average of monthly migraine days will be obtained cumulatively every 4 weeks across 52 weeks (e.g. at week 8 the average will be based on data from week 1 to week 8; at week 12 the average will be based on week 1 to week 12 and so on). The cumulative average change from baseline in monthly migraine days will be derived using difference between cumulative average of each month and baseline monthly migraine days.

The change from baseline will be analyzed using a linear mixed effects repeated measures model including treatment group, baseline value, stratification factor(s), scheduled visit, and the interaction of treatment group with scheduled visit. If applicable, in the repeated statement,

an unstructured covariance structure is assumed. Least squares means (LSMs) for each treatment group and its associated 95% confidence intervals, difference of LSMs compared to SoC treatment group and the associated 95% confidence interval of the differences, as well as the nominal two-sided p-values, will be tabulated by visit and treatment.

- Proportion of responders as measured by PGIC at month 12 on the initially assigned treatment

The Patients' Global Impression of Change (PGIC) is a global assessment by the subject of the change in clinical status since the start of treatment. The PGIC is assessed periodically through the treatment period and at the end of the treatment period. The PGIC ratings are as follows:

- 1 = No change (or condition is worse)
- 2 = Almost the same, hardly any change at all
- 3 = A little better, but no noticeable change
- 4 = Somewhat better, but the change has not made any real difference
- 5 = Moderately better, and a slight noticeable change
- 6 = Better, and a definite improvement that has made a real and worthwhile difference
- 7 = A great deal better, and a considerable difference that has made all the difference

Subject will be considered as responder if PGIC score is 5, 6, or 7 at month 12 on initially assigned treatment. Subject will be considered as non-responder if subject does not complete 12 months on initially assigned treatment or if subject does not have score 5, 6 or 7 at month 12.

Proportion of responders based on PGIC score at month 12 will be analyzed same as that of the primary endpoint.

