12.5 Analysis of secondary endpoints

12.5.1 Efficacy and/or Pharmacodynamic endpoint(s)

- Proportion of subjects completing the treatment period at month 12 on the initially assigned treatment

This variable will be analyzed same as that of the primary endpoint.

- Global satisfaction as measured by PGI at month 12 for subjects completing treatment period on initially assigned treatment

Patient will be considered as responder if PGI-I score is 5, 6, or 7. Proportion of responders based on PGI-I score at month 12 will be analyzed same as that of the primary endpoint.

- Cumulative average change from baseline on the monthly migraine days during the treatment period for subjects on the initially assigned treatment (month 1-12)

The average of monthly migraine days will be obtained cumulatively at each month across 12 months (e.g. at month 2 the average will be based on data from month 1 and 2; at month 3 the average will be based on month 1 to 3 and so on). The cumulative average change from baseline on the monthly migraine days will be derived using difference between cumulative average at each month and baseline monthly migraine days. The change from baseline will be analyzed using a linear mixed effects model including treatment group, baseline value, stratification factor(s), scheduled visit, and the interaction of treatment group with scheduled visit.

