2.5.2 Statistical hypothesis, model, and method of analysis

The primary analyses will compare the proportion of subjects in FAS who achieve a net benefit (defined in previous section) between AMG334 vs oral cycling.

Below is the hypothesis to be tested for primary analysis:

Null hypothesis: In subjects with episodic migraine, the AMG334 treatment group has the same effect as oral prophylactics group, in terms of the net benefit i.e. net benefit odds ratio =1.

Alternative hypothesis: In subjects with episodic migraine, the AMG334 treatment group is different from oral prophylactics group, in terms of the net benefit i.e. net benefit odds ratio $\neq 1$.

Randomization will be stratified by prior prophylactic migraine medication treatment failure (due to insufficient efficacy or poor tolerability) reported during screening / baseline period: 1 treatment failure (TF1) vs 2 treatment failures (TF2).

A Cochran-Mantel-Haenszel (CMH) test stratified by number of previous treatment failures (1 vs. 2) will be used under a 2-sided significance level of 0.05 to evaluate the association between the net benefit rate and the treatment. The p-value of the test, and the estimated odds ratio between AMG334 and active comparator, as well as its 95% confidence interval, will also be reported.

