5.5.2 Secondary analysis

Follow same instructions as [Section 5.5.1](#) for secondary analysis using CMH test.

Linear mixed models using repeated measurements:

The secondary endpoint of the study cumulative average change from baseline on MMD will be tested for AMG334 compared to standard of care oral prophylactics, respectively.

- Null Hypothesis: In subject with episodic migraine, the AMG334 treatment group is the same as SoC, in terms of the reduction from baseline in cumulative mean monthly migraine days in month 12
- Alternative Hypothesis : In subject with episodic migraine, the AMG334 treatment group is different as SoC, in terms of the reduction from baseline in cumulative mean monthly migraine days in month 12

It will be analyzed using a linear mixed effects repeated measures model with treatment group, baseline value, stratification factor, scheduled visit, and the interaction of treatment group with scheduled visit. In repeated statement, an unstructured covariance matrix will be used.

The test can be implemented using SAS, PROC MIXED procedure.

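### Retention and PGIC response are each tested at two-sided 0.05, and cumulative MMD change has a formal Month 12 hypothesis, but neither document says how the three secondary results are to be read together or after a failed primary.

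*SAP*

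**What the plan says.** **Primary.** SAP 2.5.2 sets one contrast, erenumab against oral prophylactics on net benefit, by stratified CMH "under a 2-sided significance level of 0.05 to evaluate the association between the net benefit rate and the treatment". No interim analysis is planned.

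**Retention.** SAP 2.7.2 introduces an odds-ratio null and alternative with "Thus, below hypothesis will be tested between initially assigned treatment groups". The method is: "A Cochran-Mantel-Haenszel (CMH) test stratified by number of prior prophylactic migraine medication failures (1 vs. 2) will be used under a 2-sided significance level of" (the level given is 0.05). Protocol 12.5.1 says of the same endpoint: "This variable will be analyzed same as that of the primary endpoint".

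**PGIC response.** SAP 2.7.2: "Proportion of responders based on PGIC score at month 12 will be analyzed same as that of the primary endpoint". Table 2-5 repeats the two-sided 0.05 level.

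**Cumulative MMD change.** SAP 2.7.2 gives a repeated-measures model, "as well as the nominal two-sided p-values, will be tabulated by visit and treatment". It states no significance level, and nor do the MMD rows of Table 2-5. SAP 5.5.2 goes further: "The secondary endpoint of the study cumulative average change from baseline on MMD will be tested for AMG334 compared to standard of care oral prophylactics," and then writes a null and an alternative for Month 12.

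**Status of the secondaries.** SAP 2.6: "There is no key secondary objective". In Protocol Table 2-1 and SAP Table 1-1 the primary objective is worded as demonstrating superiority and each secondary objective as evaluating an effect.

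Neither document contains a testing order, a gate on the primary, a division of alpha, or a statement that the secondary p-values are descriptive.

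**The concern.** Two of the three secondaries have a hypothesis, a test and a significance level, and the third has a hypothesis and a p-value. This is the form of confirmatory testing without a rule for interpreting it. Suppose the primary fails and PGIC response gives p = 0.04. That result meets the level the SAP sets for it, and nothing in the plan says it may not be reported as a significant difference.

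The question has practical weight. The protocol says the trial should inform clinicians about erenumab against oral drugs over a year, and retention, migraine days and patient-rated change are what they will look at after the primary. The open issue is whether a secondary p-value below 0.05 is a finding or a description. If that is decided after the results are known, the reader cannot tell how much chance was allowed for.

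**Working it through.** **1. The plan's own figure.** The documents give no familywise error rate for the secondaries. The only design figure tied to an alpha is the sample size in SAP section 3: 591 subjects (394:197), 90% power, odds ratio 2, control rate 0.18, two-sided 0.05.

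- Control odds: 0.18/0.82 = 0.2195. Doubled: 0.4390. Erenumab rate: 0.4390/1.4390 = 0.305, a difference of 0.125 (the SAP says 12%).
- CMH power with continuity correction, assuming a 70/30 split of strata with control rate 0.18 in both: the expected CMH numerator is 16.43, its null variance 25.48 and its variance under the alternative 22.20. Power = Φ[(16.43 − 0.5 − 1.96 × √25.48)/√22.20] = Φ(1.28) = 90.0%.

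The figure reproduces. The primary uses the full 0.05, which is proper for a single primary test, and no alpha is reserved for the secondaries.

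**2. What level each secondary carries.**

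| Endpoint | Formal hypothesis | Stated level | Status of p-value |
|---|---|---|---|
| Retention | SAP 2.7.2 | two-sided 0.05 | not labelled |
| PGIC response | by reference to the primary | two-sided 0.05 | not labelled |
| Cumulative MMD change | SAP 5.5.2, Month 12 | none | nominal, by visit |

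**3. Three tests read at 0.05, all three nulls true.**

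- Independent: 1 − 0.95³ = 0.1426, or 14.3%. The Bonferroni upper bound is 3 × 0.05 = 15%.
- With a common correlation ρ between the test statistics, the rate is 1 − ∫ [Φ((1.96 − √ρ·x)/√(1−ρ)) − Φ((−1.96 − √ρ·x)/√(1−ρ))]³ φ(x) dx.

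| ρ (assumed) | 0 | 0.3 | 0.5 | 0.7 | 0.9 |
|---|---|---|---|---|---|
| Chance of at least one false claim | 14.3% | 13.6% | 12.5% | 10.9% | 8.4% |

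**4. Only the two tests with an explicit 0.05.**

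- Independent: 1 − 0.95² = 9.75%.
- They are not independent. By the SAP's definition a subject who leaves the assigned treatment is a PGIC non-responder, so PGIC responders are a subset of retained subjects. With retention rate p and PGIC response rate q among those retained, the correlation is √[q(1 − p)/(1 − qp)].
- The documents give neither rate for this population, so p and q are assumptions. At p = 0.70, q = 0.70: √(0.21/0.51) = 0.64. At p = 0.60, q = 0.90: √(0.36/0.46) = 0.88.
- The two-test rate is 8.6% at correlation 0.64 and 7.2% at 0.88, so about 7% to 9%. Widening the assumptions to every combination of p from 0.40 to 0.70 and q from 0.60 to 0.90 gives correlations of 0.56 to 0.92 and rates of 8.9% to 6.8%, which is the same message.

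**5. What would control the rate.**

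- Fixed sequence after the primary, each step at two-sided 0.05: at most 5% overall, because a false claim requires rejection of the first true null in the sequence.
- Bonferroni among the secondaries: 0.05/3 = 0.0167 each; 1 − (1 − 0.0167)³ = 4.9% if independent.
- A gate on the primary alone is not enough. If the primary effect is real and is detected, three unordered tests of true nulls still give up to 14.3% under independence.

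**The case against.** The strongest reply is that the documents already separate the confirmatory aim from the supportive ones. Only the primary is to be demonstrated; the secondaries are to be evaluated. SAP 2.6 names no key secondary, and Protocol 8.3.2 says the trial is not considered pivotal. The 0.05 in SAP 2.7.2 is a per-test level, each test is run at that level, and no stated error rate is contradicted.

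Most of this stands, and it rules out several stronger readings that a reader might infer:

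- **That all three secondaries are tested at the full 0.05.** MMD change has no stated level, and its by-visit p-values are labelled nominal.
- **That the MMD p-values add 13 further tests at 0.05, one per four-weekly visit.** SAP 5.5.2 places the MMD hypothesis at Month 12, which SAP 1.2 equates with Week 52. The other visits carry no hypothesis.
- **That a single figure such as 12.5% replaces a promised 5%.** That value needs an assumed common correlation of 0.5, which no document supplies, and no familywise 5% is promised.
- **That PGIC p = 0.04 after a failed retention test could not be significant under any controlled procedure.** A pre-set order with PGIC ahead of retention could declare it, provided the primary had succeeded.

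What does not stand is the step from the wording of the objectives to a descriptive status. Having no key secondary ranks nothing and labels nothing. The SAP uses the word nominal for MMD and a significance level for retention and PGIC, so a reader comparing the two would conclude that the latter are meant to be judged at 0.05.

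**Conclusion.** The point holds as a gap in the decision rule, not as an error in the primary analysis. Two secondaries carry an explicit two-sided 0.05 and one carries a formal Month 12 hypothesis without a level, with nothing to say how they relate to the primary or to each other. The type I error of the primary is unaffected.

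The size is conditional on the secondaries being read as claims at 0.05 and on all their nulls being true. It is then 14.3% for three independent tests, and about 8% to 14% for assumed common correlations of 0.9 to 0. On the strictest reading, with only retention and PGIC, it is 9.75% if independent and about 7% to 9% at an assumed correlation of 0.64 to 0.88. If the sponsor reports the secondaries as descriptive, no inflation arises, but the plan does not say so. This is a cheap improvement that should be made.

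**What to change.** Choose one of two routes, before database lock.

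**Route A, if secondary claims are wanted.** Add to SAP 2.7.2:

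> Secondary endpoints are tested only if the primary is significant at two-sided 0.05. They are then tested in fixed sequence, each at two-sided 0.05: (1) retention on initially assigned treatment at Month 12; (2) cumulative average change in MMD at Week 52; (3) PGIC response at Month 12. Testing stops at the first non-significant result. Later p-values, and MMD p-values at all other visits, are descriptive.

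The order shown follows SAP 2.7.1. Protocol 12.5.1 lists PGIC before MMD, so the order is the sponsor's to choose, but it must be fixed in writing. Because treatment is open to the trial team (Protocol 6.4), keeping an order already in the documents is easier to defend than a new one.

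**Route B, if no secondary claims are wanted.** In SAP 2.7.2 and Table 2-5, replace the 0.05 significance level for the secondaries with nominal, descriptive two-sided p-values and no claim of significance.

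Under either route, align SAP 5.5.2, which sends the secondary CMH tests to the primary's instructions and states the MMD hypothesis.

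**Cost.** One paragraph, with no new data or patients and no change to the primary's alpha or power. The price of Route A is that a later secondary cannot be claimed if an earlier one fails. A failure at the retention step looks unlikely on the one-year figures the protocol cites: 75-80% for erenumab, and 13-16% for oral drugs in a chronic-migraine claims database, which is a different population. The price of Route B is that no secondary result can be called significant.
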